7.6.3.1 Phase 1b Study with SEL-212

This was a Phase 1b double-blind, sequential, single-ascending-dose study (SEL-110; Cohorts 1, 3, 5, and 7) combined with an open label, single-ascending-dose study (SEL-212; Cohorts 2, 4, 6, 10, 12 and 14) to assess the safety, tolerability, and PK of SEL-212 and SEL-110. Additionally, the study was to assess the PD (ability to reduce sUA) and immunogenicity (ability to prevent ADAs to uricase and pegadricase) of SEL-212. Generally, patients were dosed on a cohort basis in an ascending stepwise manner. A control group was dosed with SEL-037 only.

In the Phase 1b study (SEL-212/101), patients (N = 64) with a serum uric acid level \geq 6 mg/dL, with or without a history of gout, were administered SEL-110 alone, SEL-037 (pegadricase) alone, or SEL-212 (SEL-037 + SEL-110) as an intravenous infusion. Mitigation of ADAs and a dose-dependent reduction in sUA levels occurred from study Day 1 to Day 30 in patients administered SEL-212 (data on file). There was no effect of SEL-110 alone on sUA levels, and patients administered SEL-037 alone developed ADAs that resulted in loss of sUA control by Day 14. SEL-212 was generally well tolerated at all dose levels. The maximum tolerated dose of SEL-110 was determined to be 0.3 mg/kg. Data from this study were used to select additional dose levels of each component of SEL-212 for evaluation in the Phase 2 study SEL-212/201.

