8.2 Patient Exclusion Criteria

A patient who meets any of the following criteria will be excluded from this study:

1. Has a history of anaphylaxis, severe allergic reactions, or severe atopy;
2. Has a history of any allergy to pegylated products, including, but not limited to pegloticase (Krystexxa®), peginterferon alfa-2a (Pegasys®), peginterferon alfa-2b (PegIntron®), pegfilgrastim (Neulasta®), pegaptanib (Macugen®), pegaspargase (Oncaspar®), pegademase (Adagen®), peg-epoetin beta (Mircera®), pegvisomant (Somavert®) certolizumab pegol (Cimzia®), naloxegol (Movantik®), peginesatide (Omontys®), and doxorubicin liposome (Doxil®);
3. Is taking and cannot discontinue known major CYP3A4/P-gp inhibitors or major CYP3A4/P-gp inducers at least 14 days before dosing. Patients must remain off these medications for the duration of the study, including natural products such as St. John's Wort or grapefruit juice.

4. Is taking drugs known to interact with rapamycin (sirolimus - Rapamune[®]) such as cyclosporine, diltiazem, erythromycin, ketoconazole, posaconazole, voriconazole, itraconazole, rifampin, verapamil unless they are stopped 14 days prior to dosing and will not be used/prescribed during the trial.
5. Had major surgery within 3 months of initial screening.
6. Had a gout flare during Screening that was resolved for less than 1 week prior to first treatment with study drug (exclusive of chronic synovitis/arthrits) unless the patient has a history of inter-flare intervals of < 1 week.
7. Has uncontrolled diabetes at Screening with HbA1c \geq 8.5%;
8. Has fasting Screening glucose $>$ 240 mg/dL
9. Has fasting Screening triglyceride $>$ 500 mg/dL;
10. Has fasting Screening low-density lipoprotein (LDL) $>$ 200 mg/dL;
11. Has glucose-6-phosphate dehydrogenase (G6PD) deficiency;
12. Has uncontrolled hypertension defined as blood pressure $>$ 170/100 mmHg at Screening and 1 week prior to dosing
13. Individual laboratory values which are exclusionary
 - o White blood cell count (WBC) $<$ 3.0 $\times 10^9$ /L
 - o Serum aspartate aminotransferase (AST) or alanine amino transferase (ALT) $>$ 3x upper limit of normal (ULN) in the absence of known active liver disease
 - o Estimated glomerular filtration rate (eGFR) $<$ 30 mL/min/1.73 m²
 - o Urine-albumin-creatinine ratio (UACR) $>$ 30 mg/g creatinine (conventional units) or $>$ 3.39 mg/mmol creatinine (SI units)
 - o Hemoglobin (Hgb) $<$ 9 g/dL
 - o Serum phosphate $<$ 2.0 mg/dL

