14. Is receiving ongoing treatment for arrhythmia, including placement of an implantable defibrillator, unless considered stable and on active treatment;
15. Has evidence of unstable cardiovascular disease or unstable cerebrovascular disease. This includes patients who have had a cardiac/vascular event(s) in the last 3 months including heart attack, stroke or vascular bypass surgery prior to dosing or patients who are deemed, by their physician or PI, to have active cardiovascular, cerebrovascular, or peripheral vascular symptoms/disease inadequately controlled by medication;
16. Has congestive heart failure, New York Heart Association Class III or IV;
17. Unless clinically stable and/or appropriately treated, electrocardiogram (ECG) with evidence of clinically significant arrhythmia or other abnormalities that, in the opinion of the investigator, are consistent with significant underlying cardiac disease;
18. History of significant hematological disorders within 5 years or autoimmune disorders, and/or patient is currently immunosuppressed or immunocompromised;
19. Prior exposure to any experimental or marketed uricase (e.g., rasburicase (Elitek, Fasturtec), pegloticase (Krystexxa[®]), pegadricase (SEL-037))
20. Patient has received a live vaccine in the previous 6 months.

21. Patient is planning to receive any live vaccine during the study. Of note, inactivated vaccines are permitted but, study drug may affect response to vaccination; therefore, during study drug treatment vaccination with inactivated vaccines may be less effective. Consider high-dose influenza vaccine to increase the likelihood of developing a protective immune response.
22. History of malignancy within the last 5 years other than basal skin cancer;
23. Any condition, that in the opinion of the investigator, would be negatively affected by rapamycin.
24. Patients with a documented history of moderate or severe alcohol or substance use disorder within the 12 months prior to randomization.
25. History of or evidence of clinically severe interstitial lung disease
26. Immunocompromised state, regardless of etiology
27. Patients who, in the opinion of the investigator, present with a condition that would compromise their safety or that would make study completion unlikely

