11.4.6 Imaging Assessments

Multi-energy computed tomography (CT) scans will be performed at selected investigational sites as an exploratory measure to visualize monosodium urate crystal deposits and/or total body monosodium urate crystal deposits. Imaging will be conducted according to the schedule described in [Appendix A](#). The Screening assessment should be performed after preliminary determination of eligibility ([Section 8](#)) and prior to the first study drug dose on Day 0 of Treatment Period 1. Procedures for the multi-energy CT scan and analysis can be found in the Study Operations Manual.

12. ASSESSMENT OF SAFETY**12.1 Safety Parameters****12.1.1 Demographic/Medical History**

Demographic and significant medical history will be documented according to the schedule described in [Appendix A](#). Medical history will be recorded up to the time of dosing.

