An AE or suspected adverse reaction (an AE where there is a reasonable possibility that the drug caused the event; suspected drug related) is considered “unexpected” if it is not listed in the SEL-212 Investigator’s Brochure or is not listed at the specificity or severity that has been observed.

12.2.1.5 **Infusion Reactions / Adverse Events of Special Interest**

A study drug-related AE that occurs within 24 hours after initiation of study drug infusion will be assessed as an infusion reaction. An infusion reaction suspected to be anaphylaxis will be assessed according to the clinical criteria for the diagnosis of anaphylaxis based on the National Institute of Allergy and Infectious Diseases (NIAID) / Food Allergy & Anaphylaxis Network (FAAN) Symposium criteria. ([Sampson 2006](#)).

Infusion reactions will be managed and treated as described below. In addition to premedication with antihistamines and steroids ([Section 10.6.2](#)), the following steps will be implemented in this protocol to either reduce the risk of infusion reactions or manage infusion reactions.

- Patients with prior exposure to uricase therapy will be ineligible
- Patients with a history of anaphylaxis or severe allergic reactions, history of severe atopy, angioedema, or previous infusion reactions will be excluded from the trial.
- Study drug will be administered at controlled rates only in a healthcare setting and by healthcare providers sufficiently equipped and prepared to manage infusion reactions including anaphylaxis.

- In case of infusion reaction, sites will perform specific assessments as specified in the Study Operations Manual.
- Each patient will be observed for infusion reactions after dosing of study drug in the clinic for approximately 4.5 hours from the start of study drug infusion. Patients will be informed about the signs or symptoms of infusion reactions and will be instructed to notify the Investigator immediately if they believe they are experiencing a reaction.
- Each patient shall remain for a minimum of 1 hour after the completion of infusion of study drug for a period of safety observation.
- All patients will be contacted approximately 24 hours after infusion to determine whether any infusion reaction AEs occurred.
- Patients who experience an infusion reaction will be contacted approximately 24 hours after the event as follow-up.

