**3.4.2. Exclusion Criteria**

A patient who meets any of the following criteria will be excluded from this study:

1. Has a history of anaphylaxis or severe allergic reactions, or severe atopy;
2. Has a history of any allergy to pegylated products, including, but not limited to pegloticase (Krystexxa®), peginterferon alfa-2a (Pegasys®), peginterferon alfa-2b (PegIntron®), pegfilgrastim (Neulasta®), pegaptanib (Macugen®), pegaspargase (Oncaspar®), pegademase (Adagen®), peg-epoetin beta (Mircera®), pegvisomant (Somavert®), certolizumab pegol (Cimzia®), naloxegol (Movantik®), peginesatide (Omontys®), pegaptanib (Macugen®) and doxorubicin liposome (Doxil®);
3. Is taking and cannot discontinue known major CYP3A4/P-gp inhibitors or major CYP3A4/P-gp inducers at least 14 days before dosing. Patients must remain off these medications for the duration of the study, including natural products such as St. John's Wort or grapefruit juice.
4. Is taking drugs known to interact with rapamycin (sirolimus - Rapamune®) such as cyclosporine, diltiazem, erythromycin, ketoconazole (and other antifungals), nicardipine (and other calcium channel blockers), rifampin, verapamil unless they are stopped 14 days prior to dosing and will not be used/prescribed during the trial.
5. Had major surgery within 3 months of initial screening.
6. Had a gout flare during Screening that was resolved for less than 1 week prior to first treatment with study drug (exclusive of chronic synovitis/arthritis), unless the patient has a history of inter-flare intervals of < 1 week.
7. Has uncontrolled diabetes at Screening with HbA1c  $\geq 8.5\%$ ;
8. Has fasting Screening glucose  $> 240$  mg/dL
9. Has fasting Screening triglyceride  $> 500$  mg/dL;
10. Has fasting Screening low-density lipoprotein (LDL)  $> 200$  mg/dL;
11. Has glucose-6-phosphate dehydrogenase (G6PD) deficiency;
12. Has uncontrolled hypertension defined as blood pressure  $> 170/100$  mmHg at Screening and 1 week prior to dosing
13. Individual laboratory values which are exclusionary
  - o White blood cell count (WBC)  $< 3.0 \times 10^9/L$
  - o Serum aspartate aminotransferase (AST) or alanine amino transferase (ALT)  $> 3x$  upper limit of normal (ULN) in the absence of known active liver disease

This document is confidential.

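### Section 12.2.1.5 bars patients with a history of angioedema or previous infusion reactions, but no numbered exclusion criterion names either

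*Protocol*

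**What the plan says.** Protocol Section 12.2.1.5 sets out steps to reduce or manage infusion reactions. One bullet states that "Patients with a history of anaphylaxis or severe allergic reactions, history of severe atopy, angioedema, or previous infusion reactions will be excluded from the trial". The bullet before it makes patients with earlier uricase therapy ineligible. The same section defines the event: "A study drug-related AE that occurs within 24 hours after initiation of study drug infusion will be assessed as an infusion reaction".

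The numbered exclusion list appears three times, with 27 criteria each time. Criterion 1 reads "Has a history of anaphylaxis, severe allergic reactions, or severe atopy" in the protocol synopsis and Section 8.2, and "Has a history of anaphylaxis or severe allergic reactions, or severe atopy" in SAP 3.4.2. The nearest other criteria in Section 8.2 are:

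- criterion 2: "Has a history of any allergy to pegylated products, including, but not limited to" a list of named products;
- criterion 19: "Prior exposure to any experimental or marketed uricase";
- criteria 23 and 27, which leave the decision to the investigator's opinion (conditions that rapamycin would worsen; conditions that threaten safety or completion).

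**The concern.** The protocol states a safety exclusion in its adverse-event section and then leaves part of it out of the list that sites would naturally screen from. An adverse-event section is not where a screening coordinator would look for eligibility rules. A patient with past angioedema could pass all 27 criteria and receive an infused pegylated enzyme, against a rule the protocol itself calls a safeguard.

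The background data show why the safeguard is there. Section 7.6.3.2.2 reports that two of the 83 patients given SEL-212 in study SEL-212/202 had life-threatening anaphylactic reactions. Nothing links those two cases to earlier angioedema.

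There is also a bookkeeping effect. Protocol 13.3 and SAP 5.7 require eligibility deviations to be listed. Someone checking patients against the numbered list alone would not flag one with prior angioedema.

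**Working it through.** The plan gives no figure to reproduce, and no sample-size or error-rate formula applies. The check sets the bullet in Section 12.2.1.5 against the numbered lists.

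| History barred in Section 12.2.1.5 | Named in criterion 1 | Named in any other of the 27 criteria | Partial cover |
|---|---|---|---|
| Anaphylaxis | Yes | – | – |
| Severe allergic reactions | Yes | – | – |
| Severe atopy | Yes | – | – |
| Angioedema | No | No | Criterion 1 if judged a severe allergic reaction; criterion 2 if an allergy to a pegylated product; criteria 23 and 27 at discretion |
| Previous infusion reactions | No | No | Criterion 19 if the reaction was to a uricase; criterion 2 if an allergy to a pegylated product; criteria 23 and 27 at discretion |

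**Count.** Five histories are barred and three are carried over, so 5 − 3 = 2 are not. The result is the same in the synopsis, Section 8.2 and SAP 3.4.2. The SAP list is not a word-for-word copy of Section 8.2 (criterion 4 differs, for example), but its criterion 1 has the same scope.

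**Angioedema.** Remove the cases caught by criterion 1 (severe allergic reaction) and criterion 2 (pegylated product). Angioedema that was non-severe or non-allergic remains. No mandatory numbered criterion excludes it, and criteria 23 and 27 apply only if the investigator decides they do.

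**Previous infusion reactions.** Section 12.2.1.5 ties the term to study drug. On that meaning a patient must already have received study drug, and criterion 19 removes anyone given SEL-037 or another uricase. What is left is exposure to SEL-110 without the enzyme. That did occur in the Phase 1b study, where participants "were administered SEL-110 alone, SEL-037 (pegadricase) alone, or SEL-212 (SEL-037 + SEL-110) as an intravenous infusion". SEL-110.36 contains PLA-PEG, so criterion 2 arguably covers an allergic reaction to it as well. The practical remainder is close to nil.

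**Omission or intent.** The neighbouring bullet on prior uricase was carried into the list as criterion 19, while the allergy bullet was carried over only in part. That pattern suggests an oversight.

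**The case against.** **The two texts do not conflict.** Section 12.2.1.5 is mandatory and belongs to the protocol each site must follow, so applying the stricter text satisfies both. A reader might infer that the passages force opposite decisions. They do not. What stands is the narrower point that the list is incomplete.

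**Severe may qualify angioedema as well as atopy.** On that reading most of what is barred is severe angioedema, which criterion 1 largely catches. The grammar allows this, but does not require it. The ambiguity is itself a reason to name the condition in the list.

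**Section 12.2.1.5 may be the text in error.** The rationale in Section 7.6.2 speaks of severe allergies and of allergies to products resembling SEL-212, which fits criteria 1 and 2 as written. This is fair: only the sponsor can say which text was meant. Until it does, the stricter safety text should govern.

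**No rule says that sites screen from Section 8 alone.** That is correct. Section 9.2.1 cites criterion 19 by number. Section 11.4.6 refers to Section 8 when timing an exploratory CT scan: "The Screening assessment should be performed after preliminary determination of eligibility". These are cross-references and give only weak support. The point rests on what an eligibility list is ordinarily used for.

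**A reader might take previous infusion reactions to mean reactions to any infused product.** Section 12.2.1.5 does not say so, and its definition points to study drug. Writing that meaning into the list would create a new exclusion, and could class as deviators patients who broke no written rule.

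**Conclusion.** The point holds as a minor internal inconsistency with a safety consequence. Two of the five histories barred in Section 12.2.1.5 appear in none of the 27 criteria in any of the three lists. Angioedema is the one that matters, and the exposed patients are those whose angioedema was non-severe or non-allergic. The infusion-reaction omission is almost wholly covered if the term keeps the protocol's own definition.

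This assumes that the bullet in Section 12.2.1.5 is intended, that severe does not restrict angioedema, and that some sites screen from the numbered list. The number of patients with prior angioedema is not given and cannot be derived.

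A reader might infer that barred patients were dosed or that the efficacy result is compromised. The documents support neither. Premedication, controlled infusion rates and post-dose observation apply to every patient, and no endpoint, alpha or power is affected.

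**What to change.** Add angioedema to exclusion criterion 1 in the synopsis, Section 8.2 and SAP 3.4.2. Carry over previous infusion reactions in the words of Section 12.2.1.5, with no extension to other infused products unless the sponsor confirms that meaning. Notify sites. If the sponsor never intended to bar angioedema, it should correct Section 12.2.1.5 instead.

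If enrolment has closed, search the medical history for prior angioedema. SAP 8.3 has it MedDRA-coded and listed for all randomised patients. Record any such patient as an eligibility deviation when the deviation list is finalised under Protocol 13.3 and SAP 5.7. Protocol 12.1.1 asks only for significant medical history, so the search may miss minor episodes. Recording the deviation need not remove the patient from the Per Protocol Set, which excludes only major deviations affecting the primary efficacy assessment.

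The cost is slightly narrower eligibility and a protocol amendment, which Section 15.3 requires investigators to sign and the IRB/IEC to approve before it takes effect.

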12.2.2 Recording Adverse Events

Patients will be encouraged to spontaneously report any changes in health from the time of signing the ICF through completion of the study. Study staff will also inquire about any changes in the patient's health.

All AEs will be recorded in the source document and the CRF. It is the responsibility of the Investigator to review all documentation (e.g., hospital progress notes, laboratory, and diagnostics reports) for the presence of AEs and for a complete evaluation of known AEs.

At minimum for each AE, the Investigator will evaluate and report the event name/term/description, onset (date and time), resolution (date and time), event severity/intensity, relationship to study drug, action taken in regards to study drug, whether the event is an SAE, and whether or not it caused the patient to discontinue the study. The event time is only required while the patient is in the clinic.

During the Screening Phase (from time informed consent is signed to immediately before dosing) any clinically significant changes in the patient's health will be recorded in the patient's medical history and will not be considered as AEs.

12.2.2.1 Adverse Event Term/Name/Description

The Investigator will attempt to establish a diagnosis of each AE based on signs, symptoms, and/or other clinical information. In such cases, the diagnosis will be the AE term used to document the AE/SAE and not the individual signs/symptoms.

12.2.2.2 Relationship to Study Drug

The Investigator is obligated to assess the relationship between study drug and the occurrence of each AE. The Investigator will use clinical judgment to determine the relationship. Alternative causes, such as natural history of the underlying diseases, concomitant therapy, other risk factors, and the temporal relationship of the event to the study drug will be considered and investigated. The Investigator will also consult the SEL-212 Investigator's Brochure and/or Product Information for marketed products in the determination of his/her assessment.

The Investigator will assess causality as to whether the event is related or not related to study drug based on the following definitions:

- Not Related: If no valid reason exists for suggesting a relationship to study drug or the AE was more likely explained by causes other than study drug.
- Unlikely to be Related: Onset of the event has a reasonable temporal relationship to study drug administration and although a causal relationship is unlikely, it is biologically plausible.
- Possibly Related: Onset of the event has a strong temporal relationship to administration of the study drug and a causal relationship is biologically plausible
- Related: The study drug dosing and AE were closely related in time and the AE may be explained by exposure to study product: e.g., known pharmacological effect or recurrence on re-challenge.

There may be situations, particularly when an SAE has occurred, where the Investigator has minimal information to make an assessment in an initial SAE report. However, it is very important that the Investigator always makes an assessment of causality for every SAE prior to transmission of the SAE report. The Investigator may change his/her opinion of causality in light of follow-up information, amending the SAE report accordingly. Any assessment of causality made by the Investigator should also be documented in the patient's source medical record.

12.2.2.3 Adverse Event Intensity/Severity Grading

AEs will be classified according to the Rheumatology Common Toxicity Criteria, version 2.0 ([Woodworth 2007](#)).

- Grade 1 (mild): AE that is usually transient of short duration; or involves mild or minor symptoms which are of marginal clinical relevance; or is asymptomatic consisting of clinical or diagnostic observations alone; no intervention or only minimal treatment with non-prescription intervention was required. The event does not generally interfere with usual activities of daily living.
- Grade 2 (moderate): AE that is usually alleviated with additional specific therapeutic intervention. The event interferes with usual activities of daily living (e.g., shopping, laundry,

transportation, or ability to conduct finances), causing discomfort but poses no significant or permanent risk or harm to the patient.

- Grade 3 (severe): AE that is medically significant/important but not life-threatening; may require brief hospitalization to prevent the event from worsening; interrupts usual activities of daily living, or significantly affects clinical status, or may require intensive therapeutic intervention.
- Grade 4 (life-threatening): An AE, and/or its immediate sequelae, which is associated with an imminent risk of death or which is associated with physical or mental disabilities that affect or limit the ability of a person to perform activities of daily living (eating, ambulation, toileting, etc.); disability may be persistent or result in significant disability, incapacity or limitation of self-care activities.

For an assessment of anaphylaxis, the clinical criteria for the diagnosis of anaphylaxis will be based on the NIAID/FAAN Symposium criteria ([Sampson 2006](#)).

